# SYNOPSIS

## Study Title

Randomized, Double-blind, Multi-centre, Proof of Concept, Dose Finding Phase 2 Clinical Trial on ivermectin for the treatment of Covid-19.

## Design

Prospective, multi-centre, randomized, double-blind trial to assess safety and efficacy of ivermectin for the treatment of initial infection with SARS-CoV2 infection.

Study arms: A) placebo B) ivermectin 600 µg/kg daily for 5 consecutive days (I\_600) + placebo. C) ivermectin 1200 µg/kg daily on an empty stomach with water for 5 consecutive days (I\_1200). Patients will be randomized at emergency rooms of hospitals as well as at outpatient ambulatory care as well as at home, according to routine procedures of recruiting centres.

In arm A and B, the number of placebo tablets to be administered will be calculated by the study dedicated pharmacist considering the number of tablets that should be taken in case a patient with the same weight is assigned to arm C.

## Sample size

A first analysis will be conducted after enrollment of the first 60 patients (20 per arm) for safety and efficacy purpose.

Thereafter, if both experimental treatments will be compared with control group, the total number of patients to be analyzed will be 102 (129 to be enrolled).

If only one experimental group is going to be compared with control arm, the total number of evaluable patients will be 84 (105 to be enrolled).

## Inclusion Criteria

- Age ( $\geq 18$  years)
- Positivity at RT-PCR for SARS\_CoV2 (nasopharyngeal swabs)

- COVID-19 Severity Score < 3
- Patient able to take oral drugs

**Exclusion criteria:**

- Pregnant or lactating women (pregnancy test not required, in case of doubt patient is excluded)
- Subjects suffering from known CNS diseases
- Lack of (or inability to provide) informed consent
- Patient under dialysis
- Any severe medical condition with a prognosis of < 6 months
- Patients under warfarin treatment
- Patients under antiviral treatment
- Patients under chloroquine phosphate or hydroxychloroquine

**Trial duration**

Overall trial duration is expected to be approximately 6 months.

**Primary objectives**

The study is aimed

1. at defining if ivermectin, administered at dosage of 600 mcg/kg or 1200 mcg/kg QD for five consecutive days is safe in patients with initial, asymptomatic or oligosymptomatic SARS\_CoV2 infection, and:
2. at defining if ivermectin, administered at the dosage(s) found to be safe decreases the viral load of SARS-CoV2 at Day 7.

**Secondary objectives**

To assess

1. the temporal profile of viral load at baseline, day 7, 14 and 30
2. the time to clinical cure (for symptomatic patients)
3. the proportion of patients with virological clearance at day 14 and 30.
4. the hospitalization rate.
5. the COVID-19 Severity Score at day 14 and 30

---

 1 is "no limitation of activities", 2 is "limitation of activities", 3 is "hospitalized, no oxygen therapy", 4 is " hospitalized, oxygen by mask or nasal prongs", 5 is "non-invasive ventilation or high-flow oxygen", 6 is "intubation and mechanical ventilation", 7 is "ventilation + additional organ support - pressors, RRT (renal replacement therapy), ECMO (extracorporeal membrane oxygenation)", and 8 is "death".

**Analysis**

The data will be analyzed according to the intention-to-treat principle for efficacy. All randomized subjects will be included in the analysis. For safety analysis, only patients receiving at least one dose of study treatment will be included.

**Safety**

Registration of all adverse events reported by the patients, once daily.

**Routine visits and Follow-up**

Patients will be followed with telephone calls, once daily until day 5; on day 7 when they will undergo a scheduled medical visit (at hospital or as outpatients or at home according to local procedures), plus laboratory exams. A second day scheduled medical visit plus laboratory exams will take place at day 14 and a follow-up visit will take place at day 30. Study investigators will be available by telephone call for any unscheduled contact.

## ABBREVIATIONS

ADR	Adverse drug reaction
AE	Adverse event
C max	Maximum (peak) plasma drug concentration
COVID-19	Coronavirus disease 2019
DD-PCR	Digital droplet quantitative PCR
eCRF	electronic case report form
EDC	Electronic data capture
HCQ	Hydroxychloroquine
ITT	Intention to treat
PP	Per-protocol
QD	once a day
RCT	Randomized clinical trial
RSI	Reference safety information
SADR	Serious adverse drug reaction
SAE	Serious adverse event
SARS-CoV2	Severe Acute Respiratory Syndrome - Coronavirus – 2
SmPC	Summary of product characteristics
SUSAR	Suspected unexpected serious adverse reactions
TCR	Time to clinical resolution
V d	Volume distribution
WBC	White blood cells
WHO	World Health Organization

# INTRODUCTION

## ***Rationale and background***

[figure not shown]
As of 23rd April 2020, the novel betacoronavirus SARS-CoV-2 has infected more than 2'160'000 individuals, killed over 175'000 people and has spread to more than 200 countries (WHO 23April 2020), virtually all countries of the globe. So far, despite the huge number of patients and the great number of clinical trials, either concluded or underway, no convincing proof of clinical efficacy has been obtained for any of the antiviral treatments used. Hydroxychloroquine (HCQ) has been claimed to reduce the viral load and to be clinically effective, but on the basis of methodologically questioned trials (Sanders et al. 2020). However, HCQ has become the standard of care in many COVID units and is authorized for off-label use in many countries, either alone or in association with other drugs such as anti retroviral drugs. It is reasonable to hope that some of the numerous trials currently underway will produce evidence in a relatively short time. Recently, the European Medicines Agency has warned against the inconsiderate use of HCQ, because of the risk of serious side effects, and stated that "In the context of COVID-19, these medicines should only be used as part of clinical trials or in line with nationally agreed protocols." (EMA 2020).

Recently, another drug, ivermectin, has been proven effective in vitro in reducing the viral load of SARS-CoV 2 infected Vero cells by 99.98% in 48 hours (Caly et al. 2020). Ivermectin is an "old drug"(Omura 2008) extensively used on hundred millions people for over 35 years for a wide range of parasitic infections, and with a broadening range of potential indications in recent years.

Caly et al. (Caly et al. 2020) hypothesized that the antiviral action against the SARS-CoV-2 in vitro was through the inhibition of the IMP $\alpha$ / $\beta$ 1 heterodimer-mediated nuclear import of viral proteins, as shown for other RNA viruses (Tay et al. 2013; Wagstaff et al. 2012; Yang et al. 2020). However, the IC-50 for this antiviral effect was approximately 2.5  $\mu$ M, equivalent to 2,190 ng/mL, that is about 50-fold higher than the peak concentration ( $C_{max}$ ) achieved in plasma after the single dose of 200  $\mu$ g/kg, normally used as anti-parasitic drug in clinical practice (Muñoz et al. 2018; Buonfrate et al. 2019; Naquira et al. 1989). This difference raised concern on the likelihood of a successful use of ivermectin for the treatment of COVID-19 (Chaccour et al. 2020), even using doses 10-fold higher than the approved one (Schmith et al., 2020).

However, the following points suggest that five daily doses of 600 and 1200  $\mu$ g/kg in a fasted state, i.e. the schedule envisaged in the present CT, might allow to reach clinically relevant drug concentrations at the target organ (lung):

i) The results of our simulation of the plasmatic concentrations expected in patients receiving the highest dose (1200 µg/kg) in fasted state. This simulation was based on the plasma values obtained by Guzzo et al., (Guzzo et al. 2002) after single injection of 500-2000 µg/kg in fasted state, using a half-life of elimination of 35h. This value is consistent with the terminal part of the PK profile shown in (Guzzo et al. 2002), corresponds to the value determined in a recent PBPK study (Duthaler et al. 2019), and is the same used by Schmith et al., (2020) for their simulation.

The Cmax value we predict after the first 1200 µg/kg dose (230 ng/mL, 0.26 µM) is proportional to the Cmax value measured after a single dose of 600 µg/kg (105-119 ng/mL, (Smit et al. 2019)), the value measured after a single dose of 200 µg/kg (46 ng/mL, (Muñoz et al. 2018)) and the value estimated by Schmith et al., 2020 for a single dose of 200 µg/kg (27 ng/mL) according to PBPK data (Duthaler et al. 2019).

Importantly, our simulation highlights that some accumulation occurs with the five daily doses (accumulation ratio calculated on the AUC: 2.25), and that Cmax values up to 320 ng/mL (0.37 µM) can be expected in plasma after the fifth dose.

Notably, these plasmatic levels are only slightly higher than the plasmatic levels observed with single administration of 2000 µg/kg in fasted state or 500 µg/kg in fed state (248 and 260 ng/mL), which were well tolerated (Guzzo et al. 2002). Moreover, a recent systematic review and meta-analysis showed no difference in the severity of the adverse events between standard (up to 400 µg/kg) and higher doses of ivermectin (Navarro et al. 2020).

ii) The possibility that concentrations in lung are higher than those in plasma. A large volume of distribution has been reported in different species including humans (Duthaler et al. 2019; Muñoz et al. 2018). A study in cattle (Lifschitz et al. 2000) showed that, after a single subcutaneous injection of avermectin, the drug availability in lung exceeds by 2.67-fold the one in plasma (calculations on the AUC0-∞); similarly, a study in goat (Lespine et

al. 2005), showed 3-fold higher ivermectin concentrations in lung than in plasma two days after a single subcutaneous or oral administration, a difference which persisted even 7 days after. Thus, lung concentrations of  $\sim 0.7 \mu\text{M}$  ( $0.26 \mu\text{M} \times 2.67$ ) could be reached in lung after a single dose of 1200  $\mu\text{g}/\text{kg}$  in humans. Moreover, as seen above, a drug accumulation is expected after five daily doses, which could amount to 2.25-fold as estimated in plasma, up to 5.35-fold as estimated by Schmith et al., (2020) consistently with the longer elimination half-life found in cattle lung ( $\sim 80\text{h}$ , (Lifschitz et al. 2000)). According to these calculations, after five 1200  $\mu\text{g}/\text{kg}$  doses, ivermectin can reach lung concentrations of 1.6-3.7  $\mu\text{M}$ , i.e. similar to the concentration needed to inhibit the replication of SARS-CoV-2 in cells (2.5  $\mu\text{M}$ ).

Another interesting observation came from the results of a trial with ivermectin for dengue virus infection (Yamasmith 2018). In this study, 400  $\mu\text{g}/\text{Kg}$  ivermectine daily for three days showed no efficacy on clinical endpoints but it significantly affected the clearance of the NS1 antigen (a proxy of the viral load), although the active concentration on Vero cells infected with the Dengue virus was 25  $\mu\text{M}$ , i.e. much higher than that reported in SARS-CoV2 – infected cells (Caly et al. 2020),

We believe that in the current pandemic situation several risks exist that pose serious ethical concerns, as it has been already pointed out (Kalil 2020). Anecdotal reports from observational series of clinical efficacy of ivermectin (at low, standard dose) in severely ill COVID-19 patients are already coming out (Patel 2020, unpublished). Already, several different treatments have become of widespread use despite very weak, if any, evidence of efficacy. This poses even a threat to the planning of rigorous RCTs, just because these treatments have often become accepted standards of care. The appearance of a new drug in the scenario has already induced expectations and reached the general press (Newsweek 2020). The risk is that the “new” drug might enter large, Phase 3 clinical trials, and/or even enter “compassionate” use, before any preliminary indication of efficacy comes out. We believe that a first, proof of concept, dose- finding trial on a limited number of patients with mild SARS-CoV2 infection is warranted before embarking on larger trials. Antiviral drugs can probably play a role in the first phase of the infection, by reducing the viral load before clinical complications arise. A viral load reduction is a pre-requisite for a possible clinical effect, and can be measured on a reasonably small group of patients, but seems very unlikely to be obtained with the doses of the drug that are normally used for parasitic infections. This is why we intend to try higher dose schedules, 600 and 1200  $\text{mcg}/\text{kg}$ , though remaining at a much lower daily dosage compared with the maximum dose found to be safe

(Guzzo et al. 2002), and beginning with a first phase of the study that will assess the frequency of side effects, before the second phase on biological efficacy, that will only be started once safety will have been confirmed.

## **TRIAL OBJECTIVES**

### ***Primary objectives***

The study is aimed:

- 1) at defining if ivermectin, administered at dosage of 600 µg/kg or 1200 µg/kg QD for five consecutive days, is safe in patients with initial, asymptomatic or oligosymptomatic SARS\_CoV-2 infection,
- 2) at defining if ivermectin, administered at the dosage(s) found to be safe, decreases the viral load of SARS-CoV-2 at Day 7.

### ***Secondary objectives***

To assess

1. the temporal profile of viral load at baseline, day 7, 14 and 30
2. the time to clinical cure (for symptomatic patients)
3. the proportion of patients with virological clearance at day 14 and 30.
4. the hospitalization rate.
5. the COVID-19 Severity Score at day 14 and 30

## **STUDY DESIGN**

This is a multicentre, prospective, randomized, double-blind, adaptive phase II dose finding study.

Patients meeting the inclusion criteria will be asked to participate to the study and randomized in a 1:1:1 ratio to either:

- Placebo arm (arm A): placebo will be identical in appearance to ivermectin in order to preserve blinding and will be administered p.o. at empty stomach with water once daily, for 5 days

- Intervention arms: a) Ivermectin, single dose 600 µg/kg, for 5 days (I\_600) and placebo (arm B) ; b) Ivermectin, single dose 1200 µg/kg, for 5 days (I\_1200) (arm C) ); these drugs will be administered p.o. once daily, for 5 days.

In arm A and B, the number of placebo tablets to be administered will be calculated by the study dedicated pharmacist considering the number of tablets that should be taken in case a patient with the same weight is assigned to arm C.

[figure not shown]
Patients will be randomized by a centralized computer system. At randomization a treatment ID is assigned to the patient. Once a treatment ID is assigned this must not be re-assigned even in cases of errors.

Enrolled subjects will be identified by a unique subject number (patient code) that will remain consistent for the duration of the study.

Patients will be recruited at the emergency room of hospitals, and/or among asymptomatic hospital workers found positive for SARS-CoV-2 at routine screening and/or in outpatient ambulatory settings, and/or at home, if not meeting the clinical criteria for hospitalization, according to the routine procedure of each participating site. The expected duration of subjects inclusion in the study is of 3 months, or until the planned number of subjects to be enrolled will be reached.

### ***Study flow chart***

All phases of the trial will be recorded following the CONSORT statement.

## ***Patient selection***

### **Inclusion Criteria**

- Age ( $\geq 18$  years)
- Positivity at RT-PCR per SARS\_CoV-2 (nasopharyngeal swabs)
- COVID-19 Severity Score  $< 3$
- Patient able to take oral drugs
- Informed consent to study participation and to personal data treatment

### **Exclusion criteria:**

- Pregnant or lactating women (pregnancy test not required, in case of doubt patient is excluded)
- Subjects suffering from known CNS diseases
- Lack of (or inability to provide) informed consent
- Patient under dialysis
- Any severe medical condition with a prognosis of  $< 6$  months
- Patients under warfarin treatment
- Patients under antiviral treatment
- Patients under chloroquine phosphate or hydroxychloroquine

### ***Trial duration***

Overall trial duration is expected to be approximately 6 months.

### ***Primary outcomes***

1. Number of serious adverse drug reaction (SADR).
2. Quantitative viral load at Day 7 as measured by quantitative, digital droplet PCR.

NB: The primary outcome no.2., as well as all secondary outcomes, will be measured only if the number of SADR is less than 4 in at least one of the treatment arms.

---

 1 is "no limitation of activities", 2 is "limitation of activities", 3 is "hospitalized, no oxygen therapy", 4 is "hospitalized, oxygen by mask or nasal prongs", 5 is "non-invasive ventilation or high-flow oxygen", 6 is "intubation and mechanical ventilation", 7 is "ventilation + additional organ support - pressors, RRT (renal replacement therapy), ECMO (extracorporeal membrane oxygenation)", and 8 is "death".

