### **Step 1:**

#### Safety analysis

After randomisation of the first 60 evaluable patients (20 per arm) a first analysis will be performed on the 2 experimental treatments for safety purpose. Safety endpoint will be the occurrence of a SADR. Definitions are reported in the paragraph «Definition and reporting of adverse events»

A'Hern single stage design (A'Hern 2001) will be adopted. For each experimental arm, the null hypothesis that the true toxicity rate is 30% will be tested against a one-sided alternative. The null hypothesis will be rejected if  $\leq 4$  SADRs are observed in 20 patients. This design yields a type I error rate of 10% and power of 80% when the true toxicity rate is 5%.

If  $\geq 5$  SADRs are observed in one of the experimental arms, the allocation of patients to that arm will be interrupted and the study will continue for efficacy analysis only for the control arm and the other treatment arm. In case that  $\geq 5$  SADRs will be experienced in both arms the study will be stopped.

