#### Interim efficacy analyses

Two interim analyses are planned at the end of stage 1: the first for efficacy and the second for futility. For both analyses only the experimental treatments considered « safe » at first stage will be tested against the control arm. For the efficacy analysis the Haybittle–Peto boundary will be used as stopping rule (Haybittle 1971): if a probability  $\leq 0.001$  that a

difference as extreme or more as that observed at the interim analysis, between the treatments is found, given that the null hypothesis is true, then the trial should be stopped early for efficacy. In case of the probability will be greater than 0.001 the trial will continue with the stage 2 and the final analysis will be still evaluated at the level of significance without alpha error correction. The interim analysis for futility will be performed according to the conditional power analysis (Lachin 2005). The experimental arm will be stopped if, under the assumption of the results distribution of future data, calculated assuming the current trend or the alternative hypothesis, the probability of detect a statistically significant results at the end of the trial will be <20%.

**Step 2:** final efficacy analysis.

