### ***Routine visits***

Patients will be followed with telephone calls, once daily until day 5. A scheduled medical visit plus lab exams will take place at day 7, 14 and 30. Study investigators will be on call for any unscheduled telephone contact or unscheduled hospital visit.

At routine visits the following procedures will be completed:

- Laboratory tests as per routine procedures of each participating site, plus (if not included in routine): FBC, ALT at Day 7, 14 after administration of the first dose.
- Collection of any adverse events to be recorded in the eCRF
- On Day 7 and 14 a second and a third nasopharyngeal swabs will be performed for molecular analysis of SARS-CoV-2 infection. If negative at day 14, the swab will be repeated once, or not, according with routine procedures. If still positive, it will be repeated at Day 30.

When the visit includes administration of therapy (Day 1), ivermectin (or placebo) will be administered according to the randomized arm.

A clinical examination and lab/imaging exams will be carried out for subjects present at the clinical site at the time of inclusion, according to local routine. Available, relevant findings will be recorded in the eCRF.

In case of worsening of symptoms, and in consultation with the doctor ordinarily caring for home patients, the patient will be taken again to the emergency room of the recruiting site (or visited at home, or at outpatient ambulatory setting, according to the procedures of each site) and fully re-assessed, including for the need of hospitalization. In case of hospitalization, the patient will be followed according to routine procedures of each site, and each day of hospitalization will be dealt with as an unscheduled visit.

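### The rule that viral load and all secondary outcomes are measured only below 4 SADRs cannot be applied in time to Step 1 patients, conflicts with the 5-SADR stopping rule, and drops the planned by-arm comparison if both ivermectin arms fail

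*Protocol*

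**What the plan says.** The Protocol names two primary outcomes, the number of SADRs and Day 7 viral load. A note under *Primary outcomes* then states: "The primary outcome no.2., as well as all secondary outcomes, will be measured only if the number of SADR is less than 4"; the sentence goes on to require this of at least one treatment arm. The secondary outcomes covered are the viral load trend, time to clinical resolution, virological clearance, hospitalisation and the COVID-19 Severity Score.

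Other sections deal with the same count and the same data:

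- *Safety analysis* fixes when the count is taken: "After randomisation of the first 60 evaluable patients (20 per arm) a first analysis will be performed". An arm passes with 4 or fewer SADRs in 20 patients, stops with 5 or more, and the study stops if both arms have 5 or more.
- *Sample size* in the Synopsis: "A first analysis will be conducted after enrollment of the first 60 patients (20 per arm) for safety and efficacy purpose".
- *Interim efficacy analyses*: "Two interim analyses are planned at the end of stage 1: the first for efficacy and the second for futility".
- *Routine visits*: "On Day 7 and 14 a second and a third nasopharyngeal swabs will be performed for molecular analysis". No SADR condition is attached. Hospital days are recorded as unscheduled visits.
- Table 1 collects clinical data and symptoms at every visit to Day 30.
- *Statistical Analysis* analyses efficacy and secondary outcomes by intention to treat in all subjects.

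**The concern.** A rule on what is measured has to be applicable when the measurement falls due. This one depends on a count that does not yet exist when most Step 1 patients reach Day 7. Time to resolution, hospitalisation and severity cannot be measured later, and the Protocol describes no swab storage that would allow a deferred viral load assay. A site following the note and a site following the visit schedule would do different things.

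Two further consequences follow. The note uses a different cut-off from the stopping rule, so one can forbid measurement in a trial that the other continues. And if both arms fail, the note removes the planned randomised comparison of clinical course. Safety reporting does not fully replace it: under *Adverse event*, progression of the disease under study is not recorded as an AE, and under *Deaths*, a death clearly due to COVID-19 progression is documented in the eCRF but not reported as an SAE. The severity score (8 = death) and the hospitalisation rate are the planned outcomes in which worsening disease under treatment would show.

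**Working it through.** **Timing.** *Study design* expects inclusion to take 3 months, and *Statistical design and sample size* plans 129 patients. Assuming even accrual over 90 days, the rate is 129/90 = 1.43 per day and the 60th patient enters at 60/1.43 = about day 42. Patients randomised at least *d* days before then number 60 − 1.43*d*:

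- Day 7: 60 − 10 = 50
- Day 14: 60 − 20 = 40
- Day 30: 60 − 43 = 17

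So about 50 of 60 are past Day 7 when the count is taken, if it is taken at once. If it waits for the end of safety follow-up (25 days after the last dose, about Day 30), all 60 are past Day 7 and Day 14.

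**The plan's own figures.** *Safety analysis* states that "the null hypothesis that the true toxicity rate is 30% will be tested against a one-sided alternative", with a type I error of 10% and power of 80% at a true rate of 5%. By the exact binomial with n = 20:

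- Pass at ≤4 (*Safety analysis*): P(X ≤ 4 | 0.30) = 23.75%; P(X ≤ 4 | 0.05) = 99.7%.
- Pass at ≤3 (the note's cut-off): P(X ≤ 3 | 0.30) = 10.7%; P(X ≤ 3 | 0.05) = 98.4%.

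Neither gives 10% and 80%, so the stated error rates do not settle which cut-off was meant. That mismatch is a separate point.

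**Size of the conflict.** Let f4 = P(X ≥ 4) and f5 = P(X ≥ 5) in one arm of 20. I read the note's treatment arms as the two ivermectin arms, as *Safety analysis* does. I assume equal true rates, independent arms and at most one SADR per patient. Then:

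- both arms reach 4, so the note forbids measurement: f4²
- both arms reach 5, so the study stops: f5²
- measurement forbidden while the study continues: f4² − f5²

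| True SADR rate | f4 | f5 | f4² | f5² | f4² − f5² |
|---|---|---|---|---|---|
| 5% | 0.0159 | 0.0026 | 0.03% | <0.01% | 0.02% |
| 10% | 0.1330 | 0.0432 | 1.8% | 0.19% | 1.6% |
| 20% | 0.5886 | 0.3704 | 34.6% | 13.7% | 20.9% |
| 30% | 0.8929 | 0.7625 | 79.7% | 58.1% | 21.6% |

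Example at 20%: 0.5886² − 0.3704² = 0.3464 − 0.1372 = 0.2092. The 5% and 30% rows are the Protocol's own alternative and null rates.

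**One failing arm.** Exactly one arm reaches 4 with probability 2·f4·(1 − f4): 3.1%, 23.1%, 48.4% and 19.1% in the same order. In these cases the note still allows everything to be measured.

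**The case against.** The strongest reply is that the note is loose wording for a sequential plan. *Rationale and background* says the efficacy phase starts only once safety is confirmed, and if measured is taken to mean formally compared, most of the conflict disappears. Visits, swabs, eCRF entries and SAE reports proceed regardless of the count, so the raw clinical data would probably exist. At the planning rate of 5% the rule would almost never bite. All of this stands, and it limits the point.

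Two stronger readings are tempting and should not be drawn.

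- A reader might infer that Step 1 patients would never have efficacy outcomes, losing 20 of the 34 evaluable patients per arm (59%). That requires them to stay unmeasured after the condition is met. The Synopsis, the interim analyses, the swab schedule and the intention-to-treat rule all point the other way.
- A reader might infer that outcomes are discarded whenever harm is suspected. The condition fails only when both ivermectin arms reach the count; with harm in one arm, measurement goes on.

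The reply does not remove what is left. The text says measured, not compared. Under either meaning the cut-offs disagree at exactly 4 SADRs, and the by-arm comparison is dropped when both arms fail.

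**Conclusion.** The point holds in limited form. The note is a data collection rule that cannot be applied in time to most Step 1 patients and that contradicts the sections collecting and using their data. The conflict between its cut-off and that of *Safety analysis* is plain from the text and needs no assumption. Its probability does: under equal rates, independent arms and one SADR per patient at most, it is negligible at 5%, small at 10% and about one in five at 20% to 30%.

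The chance that the both-arms comparison is dropped depends strongly on which cut-off applies (34.6% against 13.7% at a 20% rate). The loss there is of the planned analysis and possibly the viral load assays, not of the clinical records. The Protocol should be corrected, but nothing here undermines the efficacy analysis of a trial in which an arm clearly passes.

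**What to change.** Delete the note under *Primary outcomes* and replace it with text to this effect:

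> Viral load and all secondary outcomes are collected in every randomised patient, from the first patient on, on the schedule under *Routine visits*, including its condition for the Day 30 swab. The Step 1 SADR result decides only whether allocation to an arm continues and whether that arm is formally tested for efficacy. If an arm or the study stops, the outcomes collected are still reported by arm with 95% confidence intervals.

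The sponsor must also reconcile the SADR cut-offs in *Primary outcomes* and *Safety analysis*, so that one rule stands in both places. Which one is for the sponsor to decide.

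The Day 30 wording matters because *Routine visits* repeats the swab then only in patients still positive; requiring every outcome at Day 30 in everyone would create a new conflict. The cost is a wording change plus DD-PCR on swabs already scheduled. The downside is assay expense for arms that do not go forward.

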Each experimental arm passing the step 1, will be compared with control arm at a statistical significant level of 0.025, one side. In this way, in case that both arms are considered for the efficacy comparison, the statistical significant level will be set to 0.025, 1 side, in order to preserve an overall family wise error of 0.05. Primary endpoint will be the difference in viral load decline from baseline to 7 days. Viral load will be measured as  $\log_{10}$  of genome copies per mL, ascertained by Digital Droplet quantitative PCR (DD-PCR). In order to calculate the sample size, we refer to data recently published on Lancet Inf. Dis. (To 2020), showing that in a population with mild disease presentation, the difference in mean viral load from baseline to 7 days is 1.05  $\log_{10}$  copies per mL (from 0.77 to 1.33  $\log_{10}$  copies, calculated from the slope and its 95%CI), with an estimated SD=0.69  $\log_{10}$  copies per mL. The desired difference in decrease between each experimental group and control is at least 0.47  $\log_{10}$  copies per mL in order to detect an effect size  $\Delta = 0.68$  (considered to be of moderate-large magnitude according to Cohen 1988). According to these hypotheses, with 34 pts per arm the study has a power=80% to detect a statistically significant difference between the experimental vs. control arm, at 0.025 alpha level, one side.

Therefore, if both experimental treatments will be compared with control group, the total number of patients to be analyzed will be 102. Considering a potential 20% loss to follow-up, it is planned to enroll 129 patients.

If only one experimental group is compared with control arm, the total number of evaluable patients will be 84 (105 to be enrolled).

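### The Step 1 safety gate has two different cut-offs, fewer than 4 SADRs and 4 or fewer, and the stated 10% type I error does not belong to the rule it is attached to

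*Protocol*

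**What the plan says.** Two places in the protocol set a numerical SADR limit that decides whether the efficacy part goes ahead.

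- **Primary outcomes, the NB.** Viral load at Day 7 and every secondary outcome "will be measured only if the number of SADR is less than 4 in at least one of the treatment arms". No number of patients is given.
- **Statistical design and sample size, Step 1, Safety analysis.** The first look comes with 20 evaluable patients per arm. For each experimental arm, "the null hypothesis that the true toxicity rate is 30% will be tested against a one-sided alternative", using the A'Hern single-stage design. The decision rule is: "The null hypothesis will be rejected if $\leq 4$ SADRs are observed in 20 patients". An arm with 5 or more is closed, and if 5 or more "SADRs will be experienced in both arms the study will be stopped". The section gives a type I error of 10% and a power of 80% at a true rate of 5%.

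Step 2 (final efficacy analysis) follows the Step 1 rule: "Each experimental arm passing the step 1, will be compared with control arm". End of Study and Procedure for the Conclusion of the Trial also allow stopping on safety grounds, but neither gives a number.

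**The concern.** The two rules differ at exactly 4 SADRs. Step 1 calls such an arm safe and Step 2 then compares it with placebo. The NB does not count it as an arm that opens the efficacy part. When no ivermectin arm is below 4 and at least one is at 4, the same data give opposite instructions.

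This is the trial's go/no-go boundary. Safety is the first primary objective, and the Rationale says that the efficacy phase starts only after safety is confirmed. If the rule is left ambiguous, someone must choose between the cut-offs once the counts are known, which is what a pre-specified boundary is meant to prevent.

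The printed type I error should show which cut-off was intended, so it was checked as well. If the two places were simply aligned at 4 or fewer and the stated 10% kept, the protocol would be consistent in wording but would still understate the risk of declaring a toxic arm safe.

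**Working it through.** **Inputs, all from Step 1, Safety analysis:** n = 20 per arm; null rate 30%; planning alternative 5%; stated type I error 10% and power 80%. Cut-offs: c = 4 (Step 1) and c = 3 (the NB, fewer than 4).

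**Assumptions.** The number of patients with a SADR in an arm is X ~ Bin(20, p), and the arms are independent. The NB refers to the same 20 Step 1 patients per arm, and its treatment arms are the two ivermectin arms.

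**1. The plan's own figures.** An arm is declared safe when X ≤ c, so the type I error is P(X ≤ c | p = 0.30) and the power is P(X ≤ c | p = 0.05).

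At p = 0.30, P(X = 0, 1, 2, 3, 4) = 0.0008, 0.0068, 0.0278, 0.0716, 0.1304. Summing up to 3 gives 0.1071, and adding the term for 4 gives 0.2375.

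| Rule (of 20) | Type I error at 30% | Power at 5% |
|---|---|---|
| ≤2 | 3.5% | 92.5% |
| ≤3 (NB) | 10.7% | 98.4% |
| ≤4 (Step 1) | 23.8% | 99.7% |
| Stated | 10% | 80% |

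The stated figures are not reproduced for the rule as written. A normal approximation does not explain the gap: for ≤4 it gives 16.5%, or 23.2% with continuity correction. At n = 20 the only cut-off near 10% is ≤3. The stated 80% power matches neither cut-off.

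**2. Where the rules collide.** Let X1 and X2 be the counts in the two ivermectin arms.

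- Step 1 stops the study only if X1 ≥ 5 and X2 ≥ 5.
- The NB blocks efficacy if X1 ≥ 4 and X2 ≥ 4.
- The conflict is therefore both counts ≥ 4 with at least one equal to 4.
- If one arm has 4 and the other has 3 or fewer, the NB is satisfied and there is no conflict.

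**3. Probability of the conflict.**

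P(conflict) = P(X1 ≥ 4)·P(X2 ≥ 4) − P(X1 ≥ 5)·P(X2 ≥ 5).

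| True rate, both arms | P(X ≥ 4) | P(X ≥ 5) | P(conflict) |
|---|---|---|---|
| 5% | 0.0159 | 0.0026 | 0.02% |
| 10% | 0.1330 | 0.0432 | 1.6% |
| 15% | 0.3523 | 0.1702 | 9.5% |
| 20% | 0.5886 | 0.3704 | 20.9% |
| 30% | 0.8929 | 0.7625 | 21.6% |

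Example at 20%: 0.5886² − 0.3704² = 0.3464 − 0.1372 = 0.2092.

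With unequal rates:

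- 5% and 20%: 0.0159 × 0.5886 − 0.0026 × 0.3704 = 0.0084, or 0.8%.
- 10% and 30%: 0.1330 × 0.8929 − 0.0432 × 0.7625 = 0.0858, or 8.6%.

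**The case against.** The best case for leaving Step 1 alone has four parts.

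- **Step 1 is the fuller statement.** It names the design, gives the denominator and states the boundary three consistent ways (pass at 4 or fewer, close at 5 or more, stop at 5 or more in both). The NB is one line and may be a slip for 4 or fewer. The stated rates are weak evidence the other way: 10.7% is above 10%, a strict 10% limit at n = 20 would require ≤2, and 80% power fits neither rule unless it is meant as a minimum. The misprint could even lie in the rates, since ≤4 of 20 gives 10.1% at a true rate of 36% and 83.0% at 15%. This stands to the extent that the documents do not prove which cut-off was intended. It does not remove the contradiction, and it does not make 10% correct for ≤4 at the 30% null that the protocol states.
- **Treatment arms might include placebo.** The protocol elsewhere uses similar terms for all three groups. The NB would then be met whenever placebo has fewer than 4. With placebo at 5%, the 20.9% above would fall to 0.2092 × 0.0159 = 0.3%. The reading is possible but unnatural: a low placebo count says nothing about whether ivermectin is safe, and Step 1 applies its test to the experimental arms only.
- **The event is rare.** It needs at least 8 affected patients among the 40 on ivermectin, and the unquantified stopping provisions could intervene first. The rarity at 5% is real. The conflict matters when both doses are more toxic than planned, which is the situation the gate is for. The wrong type I error applies to each arm regardless.
- **Samples are not lost.** Routine visits schedules the Day 7 and Day 14 swabs in any case. That is correct: what is undecided is whether efficacy is measured and Step 2 runs.

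**Conclusion.** The concern holds. The protocol fixes two incompatible cut-offs for one go/no-go decision, and nothing else in it reconciles them. The conflict is negligible at the planned 5% rate (0.02%) and reaches about one in five when both arms have true rates of 20% to 30%. Separately, the rule as written has a type I error of 23.8%, more than twice the stated 10%. The NB's cut-off comes much closer, at 10.7%.

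The conflict probabilities rest on independent arms, on 20 patients per arm as the NB's denominator, and on reading treatment arms as the two ivermectin arms. The type I error and power need only the binomial model and the figures stated in Step 1. This should be corrected before the first look at the safety data.

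**What to change.** Choose one cut-off, use it in both sections, and print the exact error rates that go with it.

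- **Preferred, because it is closest to the stated 10%.** In Step 1, declare an arm safe at ≤3 SADRs in 20, close it at ≥4, and stop the study if both arms have ≥4. Give the type I error as 10.7% and the power as 98.4% at a 5% rate. Keep fewer than 4 in the NB.
- **Alternative, if the sponsor wants 4 or fewer.** Change the NB to fewer than 5, and restate the Step 1 type I error as 23.8% and the power as 99.7%.

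In either case, add to the NB that the count is among the 20 Step 1 patients in each ivermectin arm.

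The cost is a protocol amendment, which under Ethical Aspects needs Ethics Committee approval before it is implemented. No patients or visits are added. The stricter cut-off closes an acceptable arm more often: 1.6% instead of 0.3% at a true rate of 5%, and 13.3% instead of 4.3% at 10%. In return, the chance of passing an arm with a true 30% rate falls from 23.8% to 10.7%.
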